6.2 Secondary Endpoint - Safety

The study's secondary safety endpoints are:

- Device-related* death within 48 hours (\pm 8 hours) of the procedure
- Major bleeding within 48 hours (\pm 8 hours) of the procedure
- Device-related* Clinical deterioration within 48 hours (\pm 8 hours) of the procedure
- Device-related* Pulmonary vascular injury within 48 hours (\pm 8 hours) of the procedure
- Cardiac injury within 48 hours (\pm 8 hours) of the procedure
- Mortality due to any cause within 30 days (\pm 3 days) of the procedure
- Device-related* serious adverse events within 30 days (\pm 3 days) of the procedure
- Symptomatic recurrence of embolism within 30 days (\pm 3 days) of the procedure

**Adverse Events judged as possibly related, probably related or with causal relationship to Vertex Pulmonary Embolectomy System will be considered device-related.*

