6.1 Primary Endpoint - Safety

The study's primary safety endpoint is Major Adverse Events, which is a composite of:

- Device-related death within 48 hours (\pm 8 hours) of the procedure
- Major bleeding within 48 hours (\pm 8 hours) of the procedure
- Device-related adverse events within 48 hours (\pm 8 hours), including:
 - Clinical deterioration
 - Pulmonary vascular injury
 - Cardiac injury

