7. ENDPOINT DEFINITIONS

7.1 Device-Related Death

Device-related death is defined as any death directly related to the device not performing as expected. Device-related death could include death from:

- Vascular or cardiovascular injury
- Device deficiency
- Device-induced cardiac arrhythmia
- Worsening pulmonary or right heart function (exclusive of worsening from recurrent PE)

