7.4 Clinical Deterioration

Clinical deterioration is defined by hemodynamic or respiratory worsening and will include treatment-related events, such as;

- Unplanned endotracheal intubation,
- Unexpected requirement for mechanical ventilation,
- Arterial hypotension (>1 hour or requiring vasopressors) or shock,
- Cardiopulmonary resuscitation,
- Persistent worsening in oxygenation, and
- Emergency surgical embolectomy.

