11.4 Event Relationship

The following definitions will be used to assess the relationship of the adverse event to the investigational medical device/study procedure(s):

Not related: Relationship to the device, comparator or procedures can be excluded when:

- the event has no temporal relationship with the use of the investigational device, or the procedures related to application of the investigational device;
- the (serious) adverse event does not follow a known response pattern to the medical device (if the response pattern is previously known) and is biologically implausible;
- the discontinuation of medical device application or the reduction of the level of activation/exposure - when clinically feasible - and reintroduction of its use (or increase of the level of activation/exposure), do not impact on the (serious) adverse event;
- the event involves a body-site or an organ that cannot be affected by the device or procedure;
- the (serious) adverse event can be attributed to another cause (e.g. an underlying or concurrent illness/ clinical condition, an effect of another device, drug, treatment or other risk factors);
- the event does not depend on a false result given by the investigational device used for diagnosis, when applicable;

In order to establish the non-relatedness, not all the criteria listed above might be met at the same time, depending on the type of device/procedures and the (serious) adverse event.

Possible: The relationship with the use of the investigational device or comparator, or the relationship with procedures, is weak but cannot be ruled out completely. Alternative causes are also possible (e.g. an underlying or concurrent illness/ clinical condition or/and an effect of another device, drug or treatment). Cases where relatedness cannot be assessed, or no information has been obtained should also be classified as possible.

Probable: The relationship with the use of the investigational device or comparator, or the relationship with procedures, seems relevant and/or the event cannot be reasonably explained by another cause.

Causal relationship: the (serious) adverse event is associated with the investigational device, comparator or with procedures beyond reasonable doubt when:

- the event is a known side effect of the product category the device belongs to or of similar devices and procedures;
- the event has a temporal relationship with investigational device use/application or procedures;

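### Section 7.1 defines device-related death more narrowly than the section 6.2 footnote, so a 48-hour death rated possibly related counts under one rule and not the other

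*Combined protocol and SAP*

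**What the plan says.** - **Section 6.1 (primary safety endpoint).** The composite has three parts: "Device-related death within 48 hours", major bleeding in the same window, and "Device-related adverse events within 48 hours". The last part is followed by an open-ended list: clinical deterioration, pulmonary vascular injury and cardiac injury. Device-related carries no footnote here or in the synopsis.
- **Section 6.2 (secondary safety endpoints).** The death item returns with an asterisk, "Device-related* death within 48 hours", which leads to the footnote: "Adverse Events judged as possibly related, probably related or with causal relationship to Vertex Pulmonary Embolectomy System will be considered device-related".
- **Section 7.1 (endpoint definitions).** "Device-related death is defined as any death directly related to the device not performing as expected". Four example causes follow. Only one of them is device deficiency.
- **Section 11.4 (event relationship).** The scale runs from not related through possible and probable to causal. *Possible* covers a link to use of the device, "or the relationship with procedures, is weak but cannot be ruled out completely". It also sets a default: "Cases where relatedness cannot be assessed, or no information has been obtained should also be classified as possible".
- **Section 11.5.** The investigator records the relationship to device and study procedures in one phrase. Separate ratings are not specified.
- **Sections 2.1 and 13.2.** There are at most ten subjects, and the analysis is descriptive only.

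**The concern.** Relatedness decides whether a death counts as device-related, both inside the primary composite and as an endpoint of its own. The footnote sets the threshold at *possible*. The lead sentence of 7.1 asks for a direct link and for a device that did not perform as expected. The plan does not say which prevails, and no events committee or charter is described that would settle it case by case.

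There is a second, smaller gap. The footnote asks about relatedness to Vertex, but the scale that feeds it can be met through the procedure alone. If only one joint rating is recorded, the analyst cannot tell which link the investigator had in mind.

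At stake is the reported safety count of a study in at most ten patients. If the rule is settled only after an event has occurred, a reader cannot exclude that it was chosen to fit the result.

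**Working it through.** The plan gives no sample-size, power or error-rate figure to reproduce here. The check is a comparison of rules, followed by the size of one reclassified patient.

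**Step 1. Death.** Take a patient who dies suddenly at 30 hours, with no autopsy and a cause that cannot be assessed.

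| Rule | Requirement | Device-related death? |
|---|---|---|
| 11.4 default | Not assessable | Rated *possible* |
| 6.2 footnote | Possible, probable or causal to Vertex | Yes |
| 7.1 lead sentence | Direct link to the device not performing as expected | Not shown, so no |

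The 7.1 examples include vascular injury and worsening right heart function. They suggest that malfunction in the strict sense may not be needed, so that half of the sentence can be read two ways. The gap between a direct link and a possible link remains on either reading.

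**Step 2. Does the composite change?** Often not. The third part of 6.1 is open-ended, and 7.4 lists shock and cardiopulmonary resuscitation among its examples of clinical deterioration. A death rated *possible* would often enter the composite by that route even if 7.1 kept it out of the death item.

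**Step 3. Non-fatal events.** There is no second relatedness rule for these. The question is which rating is used. Take a guidewire perforation of a major pulmonary branch, treated by endovascular means and assumed not to meet the major bleeding definition. The Terms and Definitions table classes a guidewire as an ancillary device, separate from Vertex. The footnote to section 11.2.6 lets all activities around device use be treated as procedures.

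- Joint device/procedure rating: at least *possible*, so in the composite.
- Vertex-only rating: out of the composite.

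Major bleeding does not depend on relatedness in 6.1 and is unaffected.

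**Step 4. Size per patient.** Inputs: n = 10 (section 2.1), x = 0 or 1, exact (Clopper-Pearson) 95% limits.

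- x = 0: rate 0%. Lower limit 0. Upper limit 1 − 0.025^(1/10) = 0.3085, or 30.8%.
- x = 1: rate 10%. Lower limit 1 − 0.975^(1/10) = 0.0025, or 0.3%. Upper limit is the 0.975 quantile of Beta(2, 9) = 0.4450, or 44.5%.
- Difference: 1/10 − 0/10 = 10 percentage points per disputed patient.

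**The case against.** **The composite would rarely move on a disputed death.** A reader might infer that the two death rules put the same death in or out of the primary composite. The documents do not support that as a general statement, because the open-ended third part of 6.1 would often capture it (step 2). This objection stands. The conflict falls on the death item itself.

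**A device-only count is evidently intended.** The footnote names Vertex alone. Sections 11.2.2 and 11.2.7 define adverse device events and serious adverse device effects by relation to the device, and the 11.5 reporting table uses those categories. This implies some device determination, and the eCRF, which is not part of the documents, may already hold two fields. This largely stands: the joint wording is an ambiguity, not a contradiction. It remains open because 11.4 and 11.5 never say that the device is rated by itself.

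**Many peri-procedural events are not in dispute.** A reader might infer that any event around the procedure could be counted either way. Section 11.4 allows *not related* when another cause explains the event, including a drug or another device. Hypotension attributed to sedation would leave on that ground under either reading. The same ground offers a way out for the guidewire case, so that case is only an event that could be counted either way.

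**The missing footnote in 6.1 is a formatting slip.** Probably so, since 6.2 follows at once and relists the same items. But carrying the footnote up does not resolve death, where 7.1 still conflicts.

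**Nothing is lost.** Thirty-day all-cause mortality is an endpoint, all adverse events are recorded with relationship until study exit, and deaths require source documents or a written account. This stands. The events remain visible, and only their classification is unsettled.

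**Conclusion.** The point holds in a narrow form. The 7.1 lead sentence contradicts the footnote attached to the same death endpoint. If applied as written, it would leave out deaths that the footnote counts as device-related. The missing footnote in 6.1 and the synopsis, and the joint wording in 11.4 and 11.5, are secondary ambiguities that affect the non-fatal components.

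Each disputed patient moves the affected rate by 10 percentage points, from 0/10 to 1/10. This assumes ten enrolled patients as denominator. Section 13.1 also brings procedural screen failures into the safety analysis, which would make the step smaller, and fewer than ten enrolled patients would make it larger. No test, threshold or error rate is involved.

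How often this would happen cannot be estimated. A reader might take the major adverse event rates in Table 2 of section 1.4 as a guide. They count major events as such, not events with disputed attribution, and the relatedness rules behind them are not given.

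The correction is worth making because one stated rule is wrong as written and the repair is nearly free.

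**What to change.** 1. **Section 7.1.** Replace the lead sentence with: *any death rated possibly, probably or causally related to the Vertex system*. Keep the four bullets as examples.
2. **Section 6.1 and synopsis.** Apply the 6.2 footnote to each use of device-related.
3. **Section 11.4.** State that relatedness to the device and to the procedure are rated separately, and that 6.1 and 6.2 use the device rating. List events rated as related to the procedure only on a line beside the composite.

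The cost is text edits and at most one extra field on the adverse event form, or none if the field already exists. No visits or tests are added. The downside is that, with *possible* as the threshold throughout, the primary rate may look less favourable than under 7.1 as it stands. The change should be made before outcomes are known.

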6.3 Primary Endpoint – Effectiveness

The study's primary effectiveness endpoint is the reduction in RV/LV ratio from baseline to 48 hours (\pm 8 hours or discharge, whichever occurs first) as assessed by Computed Tomography Angiography (CTA) and confirmed by qualified core laboratory.

6.4 Secondary Endpoint – Effectiveness

- Change in modified Miller Index Score between baseline and 48 hrs post procedure as assessed by CTA (core lab assessed)
- Procedural change in cardiac index
- Length of stay in the ICU associated with the index procedure
- Length of total hospital stay and post-index-procedure hospital stay
- Procedural reduction in pulmonary artery mean and systolic pressure
- Procedural reduction in Total Pulmonary Vascular Resistance
- Change in Dyspnea severity by mMRC score [Time Frame: at the 48-hour and 1-month visits]
- Change in Dyspnea severity by mMRC score [Time Frame: at the 48-hour and 1-month visits]

7. ENDPOINT DEFINITIONS

7.1 Device-Related Death

Device-related death is defined as any death directly related to the device not performing as expected. Device-related death could include death from:

- Vascular or cardiovascular injury
- Device deficiency
- Device-induced cardiac arrhythmia
- Worsening pulmonary or right heart function (exclusive of worsening from recurrent PE)

7.2 Bleeding

The Bleeding Academic Research Consortium (BARC) bleeding definitions will be used in this study.

Type 0: no bleeding

Type 1: bleeding that is not actionable and does not cause the patient to seek unscheduled performance of studies, hospitalization, or treatment by a healthcare professional; may include episodes leading to self-discontinuation of medical therapy by the patient without consulting a healthcare professional

Type 2: any overt, actionable sign of hemorrhage (eg, more bleeding than would be expected for a clinical circumstance, including bleeding found by imaging alone) that does not fit the criteria for type 3, 4, or 5 but does meet at least one of the following criteria: (1) requiring nonsurgical, medical intervention by a healthcare professional, (2) leading to hospitalization or increased level of care, or (3) prompting evaluation

Type 3

Type 3a

Overt bleeding plus hemoglobin drop of 3 to <5 g/dL* (provided hemoglobin drop is related to bleed)

Any transfusion with overt bleeding

Type 3b

Overt bleeding plus hemoglobin drop ≥ 5 g/dL* (provided hemoglobin drop is related to bleed)

Cardiac tamponade

Bleeding requiring surgical intervention for control (excluding dental/nasal/skin/hemorrhoid)

Bleeding requiring intravenous vasoactive agents

Type 3c

Intracranial hemorrhage (does not include microbleeds or hemorrhagic transformation, does include intraspinal)

Subcategories confirmed by autopsy or imaging or lumbar puncture

Intraocular bleed compromising vision

Type 4: CABG-related bleeding

Perioperative intracranial bleeding within 48 h

Reoperation after closure of sternotomy for the purpose of controlling bleeding

Transfusion of ≥ 5 U whole blood or packed red blood cells within a 48-h period†

Chest tube output ≥ 2 L within a 24-h period

Type 5: fatal bleeding

Type 5a

Probable fatal bleeding; no autopsy or imaging confirmation but clinically suspicious

Type 5b

Definite fatal bleeding; overt bleeding or autopsy or imaging confirmation

*Corrected for transfusion (1 U packed red blood cells or 1 U whole blood=1 g/dL hemoglobin).

†Cell saver products are not counted.

7.2.1 Life-threatening or Disabling Bleeding

(1) Fatal bleeding, OR

(2) Bleeding in a critical organ, such as intracranial, intraspinal, intraocular, or pericardial necessitating pericardiocentesis, or intramuscular with compartment syndrome, OR

(3) Bleeding causing hypovolemic shock or severe hypotension requiring vasopressors or surgery, OR

(4) Overt source of bleeding with drop in hemoglobin ≥ 5 g/dL or whole blood or packed red blood cells (RBCs) transfusion of ≥ 4 units*

*Given that 1 unit of packed RBC typically will raise the hemoglobin concentration by 1 g/dL, an estimated decrease in hemoglobin will be calculated.

7.2.2 Major Bleeding

The Bleeding Academic Research Consortium (BARC) Classification System Definitions will be used for this study, level 3b, 3c, 5a and 5b.

- 3b: Overt bleeding plus hemoglobin drop of ≥ 5 g/dL (provided hemoglobin drop is related to bleed); cardiac tamponade, bleeding requiring surgical intervention for control (excluding dental/nasal/skin/hemorrhoid); bleeding requiring intravenous vasoactive agents
- 3c: Intracranial hemorrhage (does not include microbleeds or hemorrhagic transformation, does include intraspinal), subcategories confirmed by autopsy or imaging or lumbar puncture, intraocular bleed compromising vision.
- 5a: Probable fatal bleeding; no autopsy or imaging confirmation but clinically suspicious
- 5b: Definite fatal bleeding; overt bleeding or autopsy or imaging confirmation

†Overt bleeding was determined by the site investigator to be bleeding visible to the eye or detectable on an imaging study

7.2.3 Minor Bleeding

Any bleeding worthy of clinical mention (e.g., access site hematoma) that does not qualify as life-threatening or disabling bleeding or major bleeding.

7.3 Recurrent PE

The Vertex Pulmonary Embolectomy System is designed to mechanically remove emboli and restore blood flow through the pulmonary arteries in patients experiencing acute PE. The goal in using this device is not 100% removal of clot but rather to remove enough clot to make a clinically significant difference in the patient. As this is a mechanical procedure where all, patients will not receive any concomitant thrombolytic therapy, new recurrence is not unexpected.

Recurrence in this study is defined as a symptomatic worsening from baseline of the embolism that was successfully treated with the index procedure. Based on the International Society on Thrombosis and Hemostasis (ISTH) guidance, "successful" means a clear clinical improvement of Subject symptoms and signs.⁴³ Symptomatic recurrent PE will be confirmed by CTA. "Symptomatic" means clinical symptoms and/or signs such as chest pains, dyspnea, hemoptysis, palpitations, or tachycardia.

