2.4 Study Population

This study will treat eligible patients with symptoms of acute PE for ≤ 14 days with CTA evidence of filling defect in one main or interlobar pulmonary artery with RV dysfunction as defined by RV/LV Ratio > 0.9 on CTA scan, as determined by investigator.

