- After removal of the Vertex Pulmonary Embolectomy System and the guidewire, continue to manage subject as medically appropriate.
- Complete the procedure per standard institutional guidelines for pulmonary artery thrombectomy procedures and transfer the subject to ICU (if appropriate) or post-surgical ward to monitor subject safety according to institutional guidelines.
- Continue to monitor for vital signs, oxygenation, and new symptoms.
- For symptomatic residual clot, distal embolization, or new PE, continue to treat with anticoagulation.
- Record adverse events/device deficiencies and technical complications as applicable.
- Post-procedure, the Investigator will review all images, clinically assessing the PE status and looking for evidence of vessel injury (perforation/dissection).
- Devices should be disposed of in accordance with applicable local regulations and site procedures following use.

The thrombectomy procedure using the Vertex Pulmonary Embolectomy System shall be aborted if the following occur in the opinion of the Investigator:

- Hemodynamic collapse
- Signs of vascular rupture

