9. STUDY VISITS

The table of study procedures and follow up visits is presented below in Table 4. All scheduled exams listed in Table 4 must be performed at the designated time point and the results documented in the EDC. The following table details the clinical and laboratory procedures required from Screening through the 30-day follow-up visit. The majority of these tests and procedures are considered standard of care for all patients under treatment of clinically significant PE.

Table 4: Schedule of Assessments

Assessment/Method	Screening/ Baseline	Procedure Day 0	Post- Procedure	48 (± 8) Hours* Follow-up Day 2	30 (± 3) Days Follow-up Day 30~ (Clinic or Phone visit)
Informed Consent	X				
Demographics	X				
Medical/Surgical History	X				
Physical Examination/Vitals	X	X ⁺	X	X	
Blood Labs (Hematocrit, Platelets, Sr creatinine, INR, BNP, Troponin, Serum lactate)	X		X		
Room Air SpO2	X			X	
mMRC dyspnea score	X			X	X
CT Angiography	X			X	
Echocardiogram	X			X	
Right heart Catheterization (Invasive Hemodynamic Assessment)		X	X		
Pulmonary Aspiration Thrombectomy		X			
Pregnancy Test	X ⁼				
Major Trauma Injury Severity Score (ISS),	X []]				
Concomitant Medications [#]	X		X	X	X
Assessment of AEs/DDs	X [^]	X	X	X	X

*or discharge; whichever occurs first = Only for females of childbearing age only who are not surgically sterilized] As applicable for subjects suspected of enduring trauma + Vitals only #Relevant concomitant medications to be documented for the study are anticoagulants, vasopressors, thrombolytics used, and all other medications given for AEs and SAEs during the study ~ 30-day visit can be completed onsite or via televisit ^ Any adverse event/device deficiency occurring since subject signed ICF will be recorded in the subject's CRF. Note: Any medical condition that is present at the time that the subject is screened will be considered as baseline and not reported as an adverse event further in the study. However, if that subject's condition deteriorates at any time during the study, it will be recorded as an AE.
					

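### As worded, the Section 7.3 definition of recurrent PE leaves some real recurrences out of the 30-day secondary safety endpoint

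*Combined protocol and SAP*

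**What the plan says.** Section 7.3 (Recurrent PE) gives the definition: "Recurrence in this study is defined as a symptomatic worsening from baseline of the embolism that was successfully treated with the index procedure". It explains success as a clear clinical improvement in symptoms and signs. It describes symptomatic by an open list of symptoms and/or signs with no severity threshold, and adds: "Symptomatic recurrent PE will be confirmed by CTA". It does not say which time point baseline refers to.

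The endpoint that uses the definition is in Section 6.2 and the synopsis. Section 6.2 words it as "Symptomatic recurrence of embolism within 30 days", with neither the reference to baseline nor the condition of successful treatment. Section 9.3.2 collects a PE recurrence rate at day 30, at a visit that may be by phone.

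Section 5, in its post-procedure steps, lists three situations separately: "For symptomatic residual clot, distal embolization, or new PE".

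**The concern.** Recurrence ordinarily means that the patient got better and then had PE again, so the natural comparison is with the state reached after treatment. Section 7.3 compares with baseline instead, and ties the event to the embolism that was treated. If baseline is the acute presentation, a patient must become worse than on admission before a recurrence is recorded. If the embolism is the treated thrombus, a fresh embolus is outside the definition.

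Both limits act in one direction: they can only lower the recurrence count. A reported rate of zero could then mean either that no recurrence happened or that those that happened did not meet the wording. Two sites could also classify the same event differently.

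**Working it through.** The documents give no recurrence rate, no split by type of recurrence and no sample-size calculation, so there is no figure of the plan's to reproduce. The check is a comparison of texts, followed by a test of how far a size can be given.

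**Step 1. What baseline means in this plan.**
- Table 4 (Section 9) heads its first column Screening/Baseline, and its note says: "Any medical condition that is present at the time that the subject is screened will be considered as baseline".
- Section 6.3 measures RV/LV reduction from baseline to 48 hours. Section 9.9.2 measures mMRC change at follow-up relative to baseline.
- Section 2.4 describes subjects at that point: "This study will treat eligible patients with symptoms of acute PE for ≤ 14 days with CTA evidence of filling defect".

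The plan's own usage is therefore the pre-procedure state, in which every subject already has symptomatic PE. Section 7.3 gives no other reference. The guidance it relies on is cited as reference 43, while the list in Section 20 ends at XXIX, so the citation does not settle the reading.

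**Step 2. Apply the definition to three CTA-confirmed, symptomatic events.**

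| Event | Baseline = screening state | Baseline = post-procedure state |
|---|---|---|
| A. Improves, then relapses, but not beyond the presenting state | Not counted | Counted |
| B. New embolus, not the treated one | Not counted | Not counted, unless embolism is read as the disease |
| C. Later distinct PE, no clear improvement after the index procedure | Not counted | Not counted |

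An illustration of A, with mMRC as the yardstick (Section 7.3 names no scale): grade 4 at baseline, 1 at 48 hours, 3 at an event on day 20. Against baseline, 3 − 4 = −1, which is no worsening. Against the 48-hour state, 3 − 1 = +2. A subject who starts at grade 4, the top of the scale in Appendix II, cannot worsen on it at all. A relapse with a sign that was absent at presentation might still qualify, because the list in Section 7.3 is broad.

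C matters because Section 5.1.3 keeps in the ITT population subjects in whom the system cannot access an embolus, and follows them for 30 days.

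**Step 3. Can the loss be sized?** Write share counted = P(clear improvement first) × P(same embolism) × P(worse than the pre-procedure state), each factor conditional on those before it. All values below are assumptions.
- Ranges: 0.70–0.95, 0.30–0.90 and 0.20–0.90.
- Lowest: 0.70 × 0.30 × 0.20 = 0.042, or 4%.
- Highest: 0.95 × 0.90 × 0.90 = 0.7695, or 77%.
- When the last two factors are both 0.90, the share is 57% to 77%. At the other grid points tried it is below 50%.

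The range is too wide to support a single figure.

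**Step 4. Effect on what would be reported.** With n = 10 (Section 2.1), assumed true 30-day recurrence p and share counted c, P(at least one counted event) = 1 − (1 − pc)^10. For p = 5% and c = 0.5 this is 1 − 0.975^10 = 22%.

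| Assumed p | All count | Half count | A quarter count |
|---|---|---|---|
| 2% | 18% | 10% | 5% |
| 5% | 40% | 22% | 12% |
| 10% | 65% | 40% | 22% |

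Under these assumptions, halving the share counted cuts the chance of seeing any recurrence by roughly 40% to 50%.

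**The case against.** The strongest reply is that Section 7.3 is ambiguous rather than wrong. The sentence presupposes a successfully treated embolism, so worsening after improvement is a natural reading, and that reading removes exclusion A. Embolism may mean the disease and not one thrombus: Section 6.2 speaks of recurrence of embolism in general, which would bring B back in. A subject who never improved has persistent PE or a treatment failure, and poor index results are captured by other endpoints. The synopsis and Section 6.2 name the endpoint while Section 7.3 defines it, so a shorter label is no contradiction. The Section 5 list is a management step, not an endpoint definition.

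Much of this stands. The alternative readings are possible, though none is written down, and the plan's consistent use of baseline points the other way. Persistent PE should indeed be kept apart from recurrence, but a later, distinct PE in a subject without initial improvement is still a recurrence of disease, and the definition has no place for it.

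The events are also not lost from the safety data. Section 11.5 records adverse events until study exit, including deterioration of a condition present at screening. Section 6.2 also counts all-cause deaths and device-related serious adverse events to 30 days. What is lost is their place in the recurrence endpoint.

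A reader might infer that most recurrences would be missed. The documents do not support that: they give no rates, and the assumed ranges run from 4% to 77% counted. Nor is there an RV/LV threshold in Section 7.3; the ratio above 0.9 is an entry criterion only.

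**Conclusion.** The point holds in a limited form. As written, and with baseline read as the plan uses it elsewhere, Section 7.3 would leave some real recurrences out of a listed secondary safety endpoint. Exclusions B and C do not depend on how baseline is read; B does depend on reading the embolism as the treated one.

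The size cannot be derived from the documents. One event moves the rate by 10 percentage points (0/10 to 1/10), but that is true of any yes/no endpoint in 10 subjects and does not measure this defect. Section 13.2 plans descriptive statistics only, so no test, sample size or decision rule is affected.

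A reader might also infer that the narrow definition flatters the primary safety endpoint, because Section 7.1 excludes worsening from recurrent PE in one of its listed examples of device-related death. The direction is the reverse. A narrow definition keeps that exclusion small, so more deaths can remain device-related; a broader definition would enlarge it unless the plan says otherwise. In the primary composite this concerns only deaths within 48 hours (± 8 hours).

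**What to change.** Reword Section 7.3 before any event is classified:

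- Set the reference point to post-procedure status: the 48-hour or discharge CTA, or the final procedural angiogram if the event comes earlier.
- Count new or worsened PE symptoms or signs together with a new or extended filling defect on the confirmatory CTA, in any pulmonary artery.
- Count these in all enrolled subjects, and report separately those without initial clinical improvement, so that persistent PE is distinguished from recurrence.
- Use the same definition for the endpoint in the synopsis and Section 6.2.
- State that the broader definition does not by itself widen the recurrent-PE exclusion in Section 7.1.

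No new scheduled assessment is needed: the 48-hour or discharge CTA, the final angiogram and the confirmatory CTA are already in the plan. The change has some cost. The confirmatory CTA has to be compared with the earlier image, which for early events is an angiogram and so a different modality. Sections 9.1.1 and 12.1 give the core laboratory RV/LV and the modified Miller score but assign no reader to this comparison, so one should be named. The reported recurrence rate may be slightly higher.
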